### 8.1 Baseline data

Baseline data will be summarised descriptively by trial arm and overall, both as randomised and as analysed. The “as randomised” population will include all participants who were randomised, but will exclude any ineligible patients randomised in error (likely to be none or very few patients). The “as analysed” population will include all participants whose data contributes to the primary analysis model (i.e. all participants who provide primary outcome data at one or more post-treatment time point). Brief baseline characteristics and treatment status of just the participants not included in the primary analysis will be presented by treatment group. No formal inferential comparisons of baseline data between

groups will be undertaken. Templates of tables used to summarise baseline data are given in Appendix D.

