### 8.2.3 Primary analysis model specification and fitting

The model fitted for the primary analysis will include all post treatment PEM scores as outcomes, modelling these using a covariance pattern model. This model will be comprised of three levels with post treatment measurement occasions ( $i = 1, 2, 3, 4$ ), nested in participants ( $j$ ), nested in centres ( $k$ ). Details of the terms included in the model are given in Table 2.

**Table 2:** Terms included in the primary analysis models. Fixed effect terms for treatment by time interactions will also be included.

Term	Interpretation	Type	Details
$\text{treat}_{jk}$	Randomised treatment group (collagenase or surgery) of the $j$ th participant at recruitment site $k$	Binary fixed effect	Indicator variable Surgery = 0, Collagenase = 1
$\text{time}_i$	$i$ th post randomisation time point	Categorical fixed effects	4 levels ( $i = 1, \dots, 4$ ) Included in model via 3 dummy indicator variables.
$\text{baseline}_{jk}$	Baseline PEM score of the $j$ th participant at recruitment site $k$ (assumed linear relationship with outcome)	Continuous fixed effect	Percentage disability (0 – 100). Missing scores will be imputed with a predicted score via regression of the observed PEM scores on the observed baseline MHQ scores and reference joint (MCP or PIP). If MHQ score is missing then baseline URAM score will be used in an analogous manner. If URAM is also missing then the reference joint strata specific mean of the observed baseline measurements will be used.
$\text{joint}_{jk}$	Designated study reference joint (MCP or PIP) of the $j$ th participant at recruitment site $k$	Binary fixed effect	Indicator variable MCP = 0, PIP = 1
$u_k$	Random intercept for recruitment site $k$	Random effect	Normally distributed with mean 0 and variance $\sigma_k^2$ . Independent across centres
$\epsilon_{ijk}$	Residual error (conditional on $b_k$ ) of the $i$ th measurement of the $j$ th participant at recruitment site $k$	Error term	$\epsilon_{jk}$ follows a multivariate normal distribution with mean 0 and covariance matrix $\Sigma_{jk}$

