### 8.3.1 Missing data

The model used for the primary analysis assumes that missing outcome data are missing at random (MAR) conditional on the fixed effects and non-missing outcomes included in the model. We will use multiple imputation to relax this MAR assumption by imputing missing values conditional on additional pre and post randomisation variables. We will also conduct analyses to investigate the sensitivity of the results to various systematic departures from MAR.

We will initially explore whether there are any obvious patterns of missingness in relation to outcome or baseline characteristics. Reasons for withdrawal and timing of withdrawal will be summarised to examine the extent to which withdrawal is driven by mechanisms plausibly related to outcome and/or treatment allocation. Unadjusted mean PEM score trajectories will be plotted for participants dropping out at each time point (both in aggregate and by allocation).

Associations between key baseline characteristics and missing outcome data and/or withdrawal prior to treatment will be explored using three sets of Firth logistic regression models [9]. Missing values of continuous baseline covariates will be mean imputed when fitting these models. The following baseline characteristics will be assessed

- Age (continuous)
- Sex (male or female)
- Smoking status (current, previous or never)
- Alcohol use (does drink alcohol or doesn't drink alcohol)
- Previous treatment with either limited fasciectomy or collagenase (previous treatment or no previous treatment)
- Presence of comorbidities (Yes or No)
- Number of digits affected (treated as continuous)
- MHQ score (continuous)
- URAM score (continuous)
- EQ-5D general health VAS score (continuous)

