### 8.3.2 Other sensitivity analyses of the primary outcome

In addition to the sensitivity analyses investigating the possible influence of missing data, a further three sensitivity analyses will be conducted, investigating the possible influence of differential delay between baseline and treatment delivery in each arm, deviations from the scheduled timing of post-treatment follow ups and an analysis adjusting for additional predictors of disease recurrence. The results of these analyses will be reported in a similar manner to the reporting of the primary analysis (Appendix E-2).

Delay between baseline and treatment delivery differs between the two arms, with participants in the surgery arm generally waiting longer between the two time points. The additional delay in the surgery

arm may lead to greater disease progression by the point of treatment delivery. Hence the baseline measurements in the surgery arm may underestimate severity of disease (at treatment) in comparison to those in the collagenase arm, meaning covariate adjustment using the baseline measurements may lead to a treatment effect estimate which is biased toward zero. Thus the treatment effect estimate from the model adjusting for baseline (as in the primary analysis) may be anti-conservative (in the context of non-inferiority). We will therefore supplement this estimate, with an estimate from a model which adjusts for the PEM measurement taken at treatment delivery (in place of the baseline measurement with all other terms remaining the same as the primary analysis). Any missing treatment delivery PEM scores will be imputed with predicted scores via regression of the observed treatment delivery PEM scores on observed baseline PEM scores and reference joint (MCP or PIP). If the baseline PEM score is also missing then the reference joint strata specific means will be used instead.

To investigate the robustness of the primary analysis to deviations from the scheduled timing of study visits/assessments, the primary analysis models will be refitted using only participants who had PEM scores collected within +/-14 days of the scheduled visit date at 3 and 6 months and within +/-91 days of the scheduled visit date at 12 and 24 months. Any missing baseline PEM scores will be imputed as for the primary analysis.

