We will investigate whether the inclusion of additional baseline predictors of recurrence has any impact on the results of the primary analysis. The primary analysis model will be refitted including four additional predictors of recurrence collected at baseline; presence/history of bilateral disease (binary), presence/history of Garrods pads, Peyronie's disease or Ledderhose disease (binary), family history (binary) and age at which the patient first experienced Dupuytren's contracture (linear term). This analysis will be based on complete cases only.

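### The diathesis-adjusted sensitivity analysis is limited to complete cases, so its comparison with the primary result mixes covariate adjustment with any change of sample

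*SAP*

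**What the plan says.** The aim in section 8.3.2 is explicit: "We will investigate whether the inclusion of additional baseline predictors of recurrence has any impact on the results of the primary analysis". The method is also explicit: "The primary analysis model will be refitted including four additional predictors of recurrence collected at baseline". The four terms are bilateral disease, a composite of Garrod's pads, Peyronie's disease and Ledderhose disease, family history, and age at first contracture. The restriction follows: "This analysis will be based on complete cases only".

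The comparator is wider. Section 8.1 describes the primary analysis population as "all participants who provide primary outcome data at one or more post-treatment time point". For a missing baseline PEM score, Table 2 in section 8.2.3 keeps the participant: "Missing scores will be imputed with a predicted score via regression of the observed PEM scores on the observed baseline MHQ scores", with URAM and then the joint-specific mean as fallbacks.

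The other two analyses in section 8.3.2 also fill in a missing PEM covariate. For the treatment-delay analysis: "Any missing treatment delivery PEM scores will be imputed with predicted scores via regression". For the visit-window analysis: "Any missing baseline PEM scores will be imputed as for the primary analysis". The missingness models in section 8.3.1 have a partial rule: "Missing values of continuous baseline covariates will be mean imputed when fitting these models".

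**The concern.** The question is what happens to the treatment estimate when covariates are added. Answering it requires the participants to be held fixed. Under complete cases, anyone lacking one of the four predictors leaves the refit but stays in the primary model. A difference between the two estimates may then come from the adjustment, from who was dropped, or from both.

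Nothing in the SAP separates these. No refit of the primary model on the reduced sample is planned. The Appendix E-2 table of estimated differences sets the diathesis row under the primary row with a single column for estimate and interval and no number analysed, so readers will compare the rows directly.

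Missing values are foreseen. Appendix D has a missing row for family history, Garrod's pads, Peyronie's disease and Ledderhose disease. For Peyronie's disease it also has a not-applicable category, and section 8.3.2 does not say how that answer enters the composite. Coded as missing, it would remove every participant who gave it.

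**Working it through.** **Inputs.** From SAP section 3: SD 22, margin 6, one-sided 2.5%, 90% power, 568 effective participants (284 per arm), 20% attrition, 710 in total. The share r dropped is not in the SAP, so it is assumed at 2, 5, 10 and 20%.

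**The plan's own figure.** The normal approximation gives 283 per arm. The noncentral t calculation gives power 0.8995 at 283 and 0.9005 at 284, so 284 per arm reproduces, and 568/0.8 = 710.

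**Standard error on the full sample.** SE = 22 × √(2/284) = 1.846, so the 95% half-width is 1.96 × 1.846 = 3.62 points.

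**Shift from the change of sample alone.** For a random subset, Var(subset estimate − full estimate) = V × r/(1 − r), with V = 22² × 2/284 = 3.408. The subset half-width is 3.62/√(1 − r).

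| Share dropped r (assumed) | N left of 568 | SD of chance shift | 95% range of shift | Half-width |
|---|---|---|---|---|
| 2% | 557 | 0.26 | ±0.52 | 3.66 |
| 5% | 540 | 0.42 | ±0.83 | 3.71 |
| 10% | 511 | 0.62 | ±1.21 | 3.81 |
| 20% | 454 | 0.92 | ±1.81 | 4.05 |

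These use the raw SD of 22. The fitted model adjusts for baseline PEM and uses repeated scores, so the true shifts would be smaller to the extent that these explain the outcome.

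**How item-level gaps add up.** If each of the four terms were missing independently in a share p, the share lost is 1 − (1 − p)⁴. For p = 1, 2, 3 and 5% this is 3.9, 7.8, 11.5 and 18.5%.

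**Net precision against the primary model.** The ratio of standard errors is about √((1 − R²)/(1 − r)), where R² is the share of residual variance that the four predictors explain. Complete-case fitting is less precise than the primary model only when r exceeds R². Against an imputed refit it is less precise under random loss at each r simulated below.

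**Simulation.** 2,000 replicates, 568 participants, a single outcome, four normal covariates with joint R² assumed at 5%, values missing at random overall, true difference zero. Mean standard errors:

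| r | Primary | Complete-case adjusted | Mean-imputed adjusted |
|---|---|---|---|
| 2% | 1.847 | 1.825 | 1.807 |
| 5% | 1.845 | 1.852 | 1.806 |
| 10% | 1.845 | 1.904 | 1.807 |
| 20% | 1.845 | 2.019 | 1.807 |

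At r = 10% the change of sample moved the estimate with SD 0.61, and adjustment on the full sample moved it with SD 0.44. The mean imputed-adjusted estimate was 0.004, so no bias was visible. At r = 2% the order reverses (0.27 against 0.44).

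**The case against.** The missing share may be small. Section 4 places randomisation after the baseline assessments are complete, and all four predictors are baseline items. At 2% the chance shift is about half a point and the comparison stays informative. This stands: the size is conditional on an assumption, and it would be wrong to say that the analysis cannot answer its question.

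Imputation is not a uniform SAP rule. The rule in section 8.3.1 covers only continuous covariates, whereas three of the four diathesis terms are binary. Section 8.4.11 drops a covariate altogether when more than 10% is missing. The visit-window analysis changes the sample on purpose. This also stands, so the point rests on the mismatch between the aim and the analysis set, not on a broken rule. In the visit-window analysis the restriction is itself the question; here it is a side effect.

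Three stronger readings are tempting, and the SAP does not support them:

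- A reader might infer that the adjustment is meant to gain precision and that the restriction defeats it. Section 8.3.2 states only a robustness aim, and net precision against the primary model falls only if r exceeds R².
- A reader might infer that complete cases means all four PEM scores present. The text refits the primary model, whose population needs only one post-treatment score, so complete on the added covariates is the natural reading.
- A reader might infer that crossing the 6-point limit in this refit would change the trial's conclusion. Section 8 bases that conclusion primarily on the primary model.

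**Conclusion.** The concern holds as a minor one. The analysis is meant to isolate the effect of adding four predictors, but its analysis set lets the sample change at the same time, with no matched refit and no number analysed in the results table. The chance shift runs from about ±0.5 points at 2% dropped to ±1.8 points at 20%, against a margin of 6. This assumes random loss, SD 22 and 284 per arm, and it overstates the shift somewhat because baseline PEM adjustment is ignored. If dropout from the refit were related to outcome, the shift need not centre on zero; the SAP gives no basis for sizing that. If nobody has a missing predictor, the problem disappears. The non-inferiority decision is not affected.

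**What to change.** Replace the complete-case sentence in section 8.3.2 with a rule that:

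- imputes missing values of the added predictors without regard to allocation: the overall mean for age at onset, and a missing-indicator category for the binary items;
- does not treat a not-applicable answer for Peyronie's disease as missing in the composite;
- fits the model to the same participants and PEM scores as the primary analysis, with baseline PEM handled as in Table 2.

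Because the predictors are collected before randomisation, imputation that ignores allocation does not bias the treatment effect.

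If complete cases are kept, state that this means complete on the added predictors, refit the primary model on the same subset, and report the number dropped by arm beside both estimates.

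The cost is a sentence or so in the SAP and a simple single imputation, or one extra model fit for the alternative. No new data are needed.

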### **8.3.3 Departures from randomised treatment**

An exploratory analysis of the primary outcome at 12 months post-treatment, will be conducted to estimate the Complier Average Causal Effect (CACE) (i.e. the average causal effect of collagenase compared with limited fasciectomy surgery in the latent principal strata of "compliers"). Compliance will be defined in terms of whether or not the randomly allocated treatment was received as part of the initial trial treatment delivery visit. Receipt of other trial and non-trial treatments following the initial trial treatment, and before providing outcome data 12 months, will be accepted as part of the treatment strategy.

Brief baseline characteristics of participants who do or do not receive the allocated treatment will be reported by allocation, as will available reasons for receiving a different treatment from the one allocated. A two-stage least squares instrumental variable estimator (assuming randomisation to be an adequate instrument) will be used to estimate the CACE. This will be implemented using Stata's `ivregress` command. Missing baseline PEM scores will be imputed following the same approach as used to impute missing baseline PEM scores for the primary analysis. Missing outcome data will be dealt with using inverse probability weighting. The probability of outcome data being non-missing at 12 months post-treatment will be estimated using a Firth logistic regression model with treatment group,

reference joint, baseline PEM score and baseline covariates associated with missingness identified previously (Section 8.3.1) as fixed effects. Estimated weights will be truncated at their 1st and 99th percentile to avoid extreme weights. The tables used to report brief baseline characteristics by compliance status and the estimate of the CACE are given in Appendix E-2.

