## **2. Design**

DISC is a multi-centre, parallel group, individually randomised controlled non-inferiority trial of collagenase injection and manipulation versus limited fasciectomy surgery for the treatment of Dupuytren's contracture. In addition to the main study, DISC contains a qualitative sub study and a photography sub study. This plan outlines the pre-specified analyses of the main trial and the photography sub study. Eligible and consenting patients will be randomised 1:1 to either collagenase injection and manipulation or limited fasciectomy surgery, using a secure randomisation service. Due to the nature of the interventions under investigation, it is not possible to blind clinicians or participants to their treatment allocation. Both treatments should be delivered within 18 weeks of randomisation (as per referral to treatment time), however where possible sites should deliver treatment within 12 weeks of randomisation. Participants will be followed up at 2 and 6 weeks post treatment and 3, 6, 12 and 24 months post treatment. A flow diagram illustrating the flow of participants through the study is presented in Appendix A.

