## **3. Sample size**

The primary outcome for DISC is the score obtained for the 11 items in part two of the PEM at 12 months post treatment. Previous survey data collected from a representative sample of 880 patients with Dupuytren's Contracture showed the standard deviation of the scores for the 11 items in part 2 of

the PEM at baseline to be 22 points (unpublished). We estimate that a 6 point difference on the PEM at 12 months post-treatment is the threshold at which differences become relevant to the patient, and represents an appropriate non-inferiority margin. An effective sample size of 568 participants (284 per arm) is required to obtain 90% power to assess non-inferiority of collagenase based on the upper limit of a two sided 95% confidence interval (CI) (equivalent to a one-sided 97.5% CI) for the treatment difference ( $\delta = \text{collagenase} - \text{surgery}$ ) at 12 months post treatment, assuming a non-inferiority margin of 6 points and a standard deviation of 22 points. This calculation is based upon the sample size needed for 90% power in a one-sided independent samples t-test of size 2.5%, of  $H_0: \delta \geq 6$  vs  $H_1: \delta < 6$ , ignoring informative baseline covariates (reference joint and baseline PEM score). If  $\delta = 6$ , then we would expect the null hypothesis that collagenase is inferior to surgery to be rejected in 2.5% of hypothetical repetitions of the trial. If  $\delta = 0$ , then we would expect the null hypothesis that collagenase is inferior to surgery to be (correctly) rejected in 90% of hypothetical repetitions of the trial (assuming an analysis based on a one sided independent samples t-test of size 2.5%). Assuming 20% attrition at the 12 month follow up, the total target sample size is 710.

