Post-treatment PEM scores (four time points)	Continuous	Percentage disability (0 – 100)	Predictive mean matching (10 nearest neighbours)
Reference joint	Binary	MCP = 0, PIP = 1	N/A (complete)
Baseline PEM score	Continuous	Percentage disability (0 – 100)	Predictive mean matching (10 nearest neighbours)
Treatment delivery PEM score	Continuous	Percentage disability (0 – 100)	Predictive mean matching (10 nearest neighbours)
Baseline URAM score	Continuous	Integer score between 0 and 45	Predictive mean matching (10 nearest neighbours)
Post-treatment URAM scores (four time points)	Continuous	Integer score between 0 and 45	Predictive mean matching (10 nearest neighbours)
Baseline MHQ score	Continuous	Overall MHQ score between 0 and 100	Predictive mean matching (10 nearest neighbours)
Post-treatment MHQ score (two time points)	Continuous	Overall MHQ score between 0 and 100	Predictive mean matching (10 nearest neighbours)
Passive extension of reference joint at baseline	Continuous	Mean of the available passive extension measurements taken of the reference joint at baseline	Linear regression
Passive extension of reference joint at treatment delivery and 3, 6, 12 and 24 months post-treatment	Continuous	Mean of the available passive extension measurements taken of the reference joint at treatment delivery and 3, 6, 12 and 24 months post-treatment	Linear regression
Active extension of reference joint at baseline	Continuous	Mean of the available active extension measurements taken of the reference joint at baseline	Linear regression
Active extension of reference joint at treatment delivery and 3, 6, 12 and 24 months post-treatment	Continuous	Mean of the available active extension measurements taken of the reference joint at treatment delivery and 3, 6, 12 and 24 months post-treatment	Linear regression
Flexion of reference joint at baseline	Continuous	Mean of the available flexion measurements taken of the reference joint at baseline	Linear regression
Flexion of reference joint at treatment delivery and 3, 6, 12 and 24 months post-treatment	Continuous	Mean of the available flexion measurements taken of the reference joint at treatment delivery and 3, 6, 12 and 24 months post-treatment	Linear regression

Crossover	Binary	Did not receive allocated treatment = 0, Received allocated treatment = 1	Logistic regression (with data augmentation if necessary)
Complications	Binary	No complication = 0, Complication = 1	Logistic regression (with data augmentation if necessary)

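### The response model behind the CACE weights (SAP 8.3.3) leaves out treatment actually received, so the estimate can be biased in either direction if 12-month response depends on receipt; minor, because the analysis is exploratory

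*SAP*

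**What the plan says.** SAP 8.3.3 plans an exploratory CACE analysis of the 12-month PEM score by two-stage least squares (2SLS), with randomisation as the instrument. A participant complies if the allocated treatment was received at the initial treatment visit.

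Missing outcomes are handled by inverse probability weighting, with this response model: "The probability of outcome data being non-missing at 12 months post-treatment will be estimated using a Firth logistic regression model with treatment group", together with reference joint, baseline PEM score and the baseline covariates found in 8.3.1 to be linked to missingness. I read treatment group as the randomised group, which is how Table 2 defines the treatment term. The weights are truncated at the 1st and 99th percentiles.

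The screening in 8.3.1 covers baseline characteristics only, so it cannot bring receipt into the weights. The multiple-imputation model for the same outcome does contain receipt: the Crossover row of Table 3 is coded "Did not receive allocated treatment = 0, Received allocated treatment = 1".

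Follow-up is timed from treatment (Section 2: "Participants will be followed up at 2 and 6 weeks post treatment and 3, 6, 12 and 24 months post treatment"). For participants who withdraw before treatment, 8.3.1 says explicitly how they are handled, both in the imputation and in the missing-not-at-random analyses. Section 8.3.3 does not mention them.

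**The concern.** The estimator divides the weighted outcome difference between arms by the weighted difference in receipt, so both parts need each arm to contain the right share of switchers. Without receipt in the response model, participants in the same arm with the same baseline covariates get the same weight whether or not they switched. If switchers respond less often, those who kept to their allocation are weighted up in their place.

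Two things follow. The difference in receipt comes out too large. The arms also lose balance on latent type: a patient who would take collagenase under either allocation is an adherer in one arm and a switcher in the other, and so is lost at different rates. If that type has a different prognosis, the CACE is biased.

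At stake is the one planned analysis of the primary outcome that allows for non-receipt. Readers of a non-inferiority trial tend to look at such an analysis, because switching can draw the arms together.

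**Working it through.** **The plan's own figure.** Section 3 gives a margin of 6, an SD of 22, one-sided 2.5% and 90% power. The normal formula is n = 2 × 22² × (1.960 + 1.282)² / 6² = 282.5, so 283 per arm. The exact t-test has 89.95% power at 283 and 90.05% at 284, so 284 per arm (568) is reproduced, and 568 / 0.80 = 710. The point does not rest on these figures.

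**Inputs that the SAP does not give (assumed).** 15% of patients would take collagenase under either allocation (type A), 3% would take surgery under either (type N), and 82% comply (type C). Response at 12 months is 85% in those who received their allocated treatment and 60% in switchers. The true effect in compliers is 6 points. On the same treatment, type A patients differ from compliers by d points, with d from -10 to +10; type N patients do not differ. Baseline covariates are taken not to predict switching.

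**Shares under the planned weights.** Without receipt in the model, weights are constant within an arm, so the weighted arm has the composition of its responders.

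- Collagenase arm: C 0.82 × 0.85 = 0.697; A 0.15 × 0.85 = 0.1275; N 0.03 × 0.60 = 0.018; total 0.8425. Shares: C 0.827, A 0.151, N 0.021. Received collagenase: 0.979.
- Surgery arm: C 0.697; N 0.03 × 0.85 = 0.0255; A 0.15 × 0.60 = 0.090; total 0.8125. Shares: C 0.858, N 0.031, A 0.111. Received collagenase: 0.111.

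**First stage.** 0.979 - 0.111 = 0.868. The true value is 0.97 - 0.15 = 0.82.

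**CACE.** The outcome difference is 6 × 0.868 + d × (0.1513 - 0.1108). Dividing by 0.868 gives 6 + 0.0467 × d:

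| d | CACE, planned weights | CACE, receipt by arm in weights |
|---|---|---|
| -10 | 5.53 | 6.00 |
| 0 | 6.00 | 6.00 |
| +10 | 6.47 | 6.00 |

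With receipt by arm in the weights, both arms return to 82/15/3, the first stage is 0.82 and the term in d cancels.

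**Wider range.** A second set of assumptions had non-adherence of 5-20% in the collagenase arm and 0-5% in the surgery arm, response of 20-80% in non-adherers with overall response held at 80%, a true effect of 0 or 6, and outcome differences of -10, 0 or +10. The bias ran from about -1.45 to +1.15 points (1.45 / 6 = 0.24 of the margin). It was zero throughout when response was 80% regardless of receipt.

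**Cost in precision.** One example was simulated with 1,000 trials of 710 participants: 15% and 5% non-adherence, 40% response in non-adherers against 84% in adherers, non-adherers 10 points worse, true CACE 0, ordinary logistic regression in place of Firth. Adding receipt by arm moved the mean CACE from -0.54 to 0.06 and raised its SD from 1.95 to 2.22 (2.22 / 1.95 = 1.14).

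**Never-treated participants.** Now assume 83% C, 5% A, 2% N and 10% who take collagenase if allocated to it but are never treated if allocated to surgery. Types A and never-treated both differ by d = -10 to +10. The planned weights give 4.83 to 7.17. Adding receipt by arm and fitting 2SLS among treated participants gives 4.98 to 7.02. So 1.02 of the 1.17 points of bias, about 87%, remains.

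**The case against.** The strongest case against has four parts.

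- **No rates.** The SAP gives no crossover rate and no response by receipt. A reader might infer that non-adherers are known to be the likeliest to be missing. The SAP does not say so. For participants never treated it follows from timing follow-up from treatment; for switchers it is an assumption. Screened baseline covariates may also recover part of any dependence. This stands.
- **Size and accuracy.** At 284 per arm the unadjusted CACE has a standard error of about 22 × √(2/284) / 0.82 = 2.25 points, so a bias of 0.47 is about a fifth of it. In the simulated example the root mean squared error rises with the fix: √(0.54² + 1.95²) = 2.02 against √(0.06² + 2.22²) = 2.22. This stands as a reason to report both estimates. It is no reason to leave an avoidable bias unexamined.
- **The never-treated range.** A reader might take a CACE of about 4.8 to 7.2, on both sides of the 6-point margin, as evidence for adding the covariate. It is not. It straddles 6 because the true effect was set at 6, and most of it remains after receipt is added. If only the always-collagenase patients differ, the range is 5.9 to 6.1.
- **Low weight in the decision.** The CACE is labelled exploratory, and non-inferiority is judged on the primary model. Baseline characteristics by receipt and reasons for switching are reported anyway. This stands and limits the severity.

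None of this explains why receipt is in the imputation model and absent from the weights of the analysis that is about receipt.

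**Conclusion.** The omission is real and is inconsistent with Table 3. Its effect is conditional. It needs 12-month response to depend on receipt given the baseline covariates and, in the worked scenario, switchers whose prognosis differs from that of compliers. Under the assumed rates the first stage is 0.87 instead of 0.82 and the CACE is about 5.5 to 6.5 against a true 6. The sign is not fixed, so it should not be inferred that the weighting favours a non-inferiority claim; the dilution from switching in an intention-to-treat comparison is a separate matter.

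Never-treated participants are a second gap, which the covariate does not close. They have essentially no chance of a 12-month post-treatment score, so no weighting can represent them. Restricting 2SLS to treated participants conditions on a post-randomisation event. The chance of reaching treatment may differ by arm, since the SAP expects longer waits for surgery, and the restriction does not remove the bias.

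Severity is minor: one exploratory analysis is affected, and the primary conclusion is not.

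**What to change.** In SAP 8.3.3:

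1. Add treatment received (allocated or other) and its interaction with allocation to the Firth response model. Report the estimate with the current weights beside it.
2. Keep never-treated participants in the CACE. Impute their 12-month score over the +/-10 range that 8.3.1 already applies to all randomised patients, and state how their receipt is coded in the first stage. The result is a range of answers rather than a single corrected estimate.
3. If a treated-only version is also wanted, label it a sensitivity analysis and state that it conditions on a post-randomisation event.

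The cost is a few sentences and some table rows. Receipt is already needed to define compliance, so no new data are required. The estimate with receipt in the weights will be more variable: the SD was about 14% higher in the simulated example.
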